Men with localized intact PCa, or non-metastatic recurrence following prostatectomy, and prescribed radiation therapy (XRT) with or without concomitant ADT will be consented and enrolled on this prospective trial. Eligible subjects are men > 18 years old diagnosed with non-metastatic PCa planning to undergo curative-intent therapy. Men with prior cardiac stent or bypass surgery will be excluded. Men with prior exposure to ADT will be excluded.

Each patient will undergo external beam XRT with or without concomitant ADT of 6-24 months duration. **For those men with National Comprehensive Cancer Network (NCCN)-defined unfavorable intermediate- or high-risk disease, or with biochemically recurrent PCa requiring salvage XRT plus ADT, each will be randomized 1:1 between injectable intramuscular or subcutaneous GNRHa depot (leuprolide 22.5 mg every 3 months, leuprolide 45 mg every six months) versus GNRH-antagonist (oral relugolix 360 mg loading dose followed by 120 mg daily).** Men with NCCN-defined low- or favorable intermediate-risk intact disease, or those with biochemically recurrent PCa requiring salvage XRT without ADT, will be treated with XRT alone. Each patient will provide consent for (1) pre-treatment and 12-month post-ADT prospective ECG-gated, contrast-enhanced CCTA and (2) peripheral blood banking at baseline and at 3-, 6-, and 12-months post-treatment (**Figure 5**).

Figure 5. Study Schema

ADT randomization will be created using preconstructed allocation sequences using maximal randomization (<https://ctrandomization.cancer.gov/tool/>). Patients will undergo a pre-randomization stratification based on Atherosclerotic Cardiovascular Disease (ASCVD) risk score (low/intermediate versus high). All principal investigators and co-investigators will be blinded to this randomization block. Lead statistician ([name]) and clinical research coordinators will have access to this allocation sequence.

Methods: As seen in above study schema, each patient in each cohort will undergo pre-treatment and 12-month post-ADT initiation coronary CT. Each patient will undergo a non-contrast CT scan using standard

Protocol Title: Mechanism and Predictors of Cardiotoxicity after Prostate Cancer Treatment: A Parallel Cohort and Randomized Trial Comparing Radiation Alone, Radiation plus Leuprolide, and Radiation plus Relugolix

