coronary artery calcium (CAC) imaging protocol for coronary calcium quantification prior to the acquisition of the CCTA. CAC images will be obtained using prospective ECG-triggering at 70% of the R-R interval, using tube voltage of 120 kV and an automated tube current modulation and minimum slice collimation (0.6 mm). Images will be reconstructed in 3 mm slice thickness at 3 mm intervals. Following CAC scan, contrast-enhanced CCTA will be performed using an ECG-gated, single-beat acquisition scan to include 30-80% of the R-R interval. Scanning will extend from the tracheal bifurcation to 2 cm below the left ventricular apex; 0.5 mm detector collimation will be used.

Additionally, peripheral blood will be drawn and stored in our established biorepository (under protocol WINSHIP5179-20) at the following intervals: pre-treatment, and 3-, 6-, and 12-months post-ADT initiation. Further details regarding analysis plan of peripheral blood below in Aims 2 and 3.

Aim 1.1: To determine the relationship between ADT (i.e. GNRHa versus relugolix) and accelerated coronary plaque development and/or rupture in PCa men, all contrast enhanced CCTA images will be analyzed using a commercially-available, validated artificial intelligence-guided imaging analysis service (HeartFlow, Inc, Mountain View CA). Multiplanar reconstructed images will be assessed for the presence, volume, and qualitative composition (e.g. total, calcified, non-calcified, mixed) of atherosclerotic plaque for each coronary artery segment. Luminal stenosis will be graded on an ordinal scale 0-100%. CCTA scans pre- and 12 months post-treatment will be compared. We hypothesize that ***men receiving GNRHa will be at increased risk of total plaque volume increase compared with men receiving relugolix or no ADT.***

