Analysis Plan: We will measure coronary plaque volume using CCTA images at both baseline and 12-months post-treatment initiation. The primary endpoint will be (1) total coronary plaque volume (continuous). Secondary endpoint will be non-calcified coronary plaque volume (continuous). Other outcome measures include (1) calcified plaque volume (continuous), (2) low-attenuation plaque volume (continuous), (3) coronary artery calcification score (continuous), and (4) coronary vessel stenosis (ordinal). The change in endpoint metrics between baseline and 12-month will be estimated for leuprolide versus relugolix versus no ADT. Data transformation to fit statistical assumptions will be done as needed. In addition, we will implement multivariable models that control for potential confounders (e.g. age, statin medication use) using general linear regression and/or logistic regression.

Power: We hypothesized that there will be significantly greater total plaque burden (i.e. summation of total plaque volume of all major coronary territories) increase from baseline to month 12 following GNRHa versus no ADT or relugolix. Using a standard deviation of 30 mm³ for the change in total plaque volume from scans obtained at two time points approximately 12 months apart in the study, 60 participants (30 in each comparative treatment arm) with both baseline and month 12 CCTA would provide 80% power to detect a difference of ≥ 20 mm³ in the change in total plaque volume [$P(X>Y) 0.72$] from baseline to 12 months.

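### Aim 1 should name GNRHa versus relugolix as its one primary contrast and adjust it for baseline plaque and the ASCVD randomisation stratum, at almost no cost

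*Combined protocol and SAP*

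**What the plan says.** All references are to the combined protocol and SAP.

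- **Main comparison** (section 6, Aim 1, Analysis Plan). The primary endpoint is total coronary plaque volume, and "The change in endpoint metrics between baseline and 12-month will be estimated for leuprolide versus relugolix versus no ADT". No test or model is named for this step.
- **Covariates** (same paragraph). Further multivariable models are to "control for potential confounders (e.g. age, statin medication use) using general linear regression and/or logistic regression". Age and statin use are given as examples only.
- **Scale** (same paragraph). "Data transformation to fit statistical assumptions will be done as needed".
- **Hypothesis** (section 6, Aim 1.1 and Power). Aim 1.1 expects that "men receiving GNRHa will be at increased risk of total plaque volume increase compared with men receiving relugolix or no ADT". The power paragraph expects a greater plaque "increase from baseline to month 12 following GNRHa versus no ADT or relugolix".
- **Power** (section 6, Aim 1, Power). "60 participants (30 in each comparative treatment arm) with both baseline and month 12 CCTA would provide 80% power" for a difference of 20 mm³ with an SD of change of 30 mm³. The two arms are not named, and no alpha or sidedness is given.
- **Randomisation** (section 6). "Patients will undergo a pre-randomization stratification based on Atherosclerotic Cardiovascular Disease (ASCVD) risk score (low/intermediate versus high").
- **The no-ADT group** (section 6). "Men with NCCN-defined low- or favorable intermediate-risk intact disease, or those with biochemically recurrent PCa requiring salvage XRT without ADT" receive radiation alone, so this group is formed by indication and not by randomisation.
- **Emphasis elsewhere.** Section 1 describes a randomised trial with a parallel cohort. The main goal in section 2 and the title of Aim 1 in section 4 set the GNRH agonist against relugolix.

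**The concern.** Two matters are left open that could be settled before any outcome data are seen.

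The first is precision. The trial has 30 men per randomised arm and a continuous endpoint. Baseline plaque volume and the ASCVD stratum will be known for every randomised man, and the plan itself gives some reason to think such variables matter: it stratifies on ASCVD risk, and Subaim 1.2 (section 9) asks whether baseline imaging biomarkers correlate with plaque development. Subaim 1.2 is a question about predictors, however, and does not adjust the arm comparison. If these variables do predict plaque change, leaving them out of the main comparison discards information already paid for.

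The second is which comparison carries the primary claim. The hypothesis can be read as supported by GNRHa versus relugolix or by GNRHa versus no ADT. The second contrast compares men who differ in cancer risk group or in the indication for salvage treatment, so a difference may reflect selection and not the drug. With no ranking, a positive non-randomised contrast could be reported as confirming the hypothesis when the randomised contrast does not.

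**Working it through.** **Inputs.** From the power paragraph: n = 30 per arm with both scans, difference 20 mm³, SD of change 30 mm³. Assumed, because the documents do not give them: alpha 5% (two-sided, with one-sided shown), a normal outcome, and r, the correlation of baseline plaque and stratum taken together with the 12-month change.

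**Step 1: the plan's own figure.** The standard error is 30 × √(2/30) = 7.75 mm³ and the noncentrality is 20/7.75 = 2.58, with 58 degrees of freedom.
- Two-sided 5%: power 71.9% (t-test), 69.0% (simulated Wilcoxon).
- One-sided 5%: power 81.8% (t-test), 79.8% (simulated Wilcoxon).

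The stated 80% is therefore reproduced at one-sided 5%, which the plan does not state, and not at two-sided 5%.

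**Step 2: adjustment by formula.** The residual SD is 30 × √(1 − r²). At r = 0.3 this is 28.6 and the noncentrality is 2.71; at r = 0.5 it is 26.0 and 2.98. Two-sided power at r = 0, 0.2, 0.3, 0.4 and 0.5 is 71.9%, 73.6%, 75.9%, 79.1% and 83.4%.

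**Step 3: adjustment by simulation.** The formula ignores chance imbalance in the covariates. An ANCOVA with arm, baseline and stratum fitted was compared with an unadjusted t-test in the same data (two-sided 5%, half of each arm in the high stratum, 100,000 runs per cell):

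| r | Unadjusted | Adjusted | Change (points) | Adjusted 95% CI half-width (mm³) |
|---|---|---|---|---|
| 0 | 72.1% | 71.3% | −0.8 | 15.6 |
| 0.2 | 72.1% | 72.9% | +0.8 | 15.3 |
| 0.3 | 72.4% | 75.1% | +2.7 | 14.9 |
| 0.4 | 72.6% | 78.4% | +5.8 | 14.3 |
| 0.5 | 72.9% | 82.6% | +9.7 | 13.5 |

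The unadjusted half-width is about 15.5 mm³. Break-even lies near r = 0.14. With 30% or 20% of men in the high stratum, adjusted power from r = 0.2 upwards agrees within 0.3 points, and the loss at r = 0 stays between 0.7 and 0.9 points. At one-sided 5%, adjusted power for the same five values of r is 81.3%, 82.5%, 84.2%, 86.7% and 89.9%, against 81.8% unadjusted at r = 0.

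**Step 4: ignoring the stratum.** Take 30% of men in the high stratum, strata balanced between arms, and a difference in mean change of 15 to 30 mm³ between strata (all assumed). The true type I error of the unadjusted t-test then falls to about 4.2% to 2.7%. It is conservative, not inflated.

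**Step 5: two unranked contrasts.** Both contrasts share the GNRHa arm. With equal arms and equal variances their correlation is (σ²/30)/(2σ²/30) = 0.5. If each is tested at two-sided 5%, the chance of at least one false positive is about 9.1% by simulation; independent tests would give 1 − 0.95² = 9.75%. This counts chance alone and no confounding. The only multiplicity rule in the document, Holm-Bonferroni, is in the Aim 2 plan.

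**The case against.** **The plan already leans the right way.** Sections 1, 2 and 4 put GNRHa versus relugolix first, and the sample-size line in section 1 uses arm for the randomised groups and cohort for the no-ADT men. This supports reading the 60 men in the power paragraph as the randomised pair. It stands as a reading but does not settle the matter: sections 9 and 12 use arm for all three groups, and neither the hypothesis nor the analysis plan ranks the contrasts.

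**Nothing is excluded.** The covariate list is open, so a reader who infers that the plan rules out baseline plaque or ASCVD risk goes beyond the text. That the main comparison is unadjusted is also an inference, from models being introduced as an addition. Both points stand. What can be said is that these covariates are not pre-specified.

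**The gain may be small.** This stands too. The documents give no r, and the imaging biomarkers of Subaim 1.2 are not identified as total plaque volume. Below about r = 0.14 adjustment loses slightly; material gains need r of 0.4 or more. At one-sided 5% the stated power is met without covariates.

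**A rank method may be what was intended.** The power sentence carries a P(X>Y) of 0.72, an effect size of the rank-test kind, and the plan foresees transformation. With skewed data the choice of method can outweigh the covariates. In one assumed illustration (lognormal errors with sigma 0.8, SD 30, shift 20, two-sided 5%), ANCOVA has about 75% power at r = 0 and 78% at r = 0.3, against about 98% and 96% for an unadjusted Wilcoxon test; with normal data the Wilcoxon has 69%. There is thus no ground for relegating rank methods to sensitivity analysis.

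**Conclusion.** The point holds as a cheap improvement to pre-specification, one that should be made; it is not a flaw that undermines the trial. Baseline total plaque volume and the ASCVD stratum are unnamed in the Aim 1 comparison, and the randomised and non-randomised contrasts are unranked in the hypothesis.

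The ranking part is the firmer of the two, because it needs no assumed correlation. Its size is about 9.1% family-wise error if both contrasts are tested at 5%, plus confounding that cannot be quantified from the documents. The covariate part is worth between −0.8 and about +10 power points for r between 0 and 0.5, assuming normal data, two-sided 5% and 30 completers per arm.

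Two stronger readings are not supported. A reader might infer that the unadjusted randomised comparison is biased or invalid; randomisation protects it, and ignoring the stratum errs on the conservative side. A reader might also infer that adjustment is needed to rescue a failed power calculation. The shortfall appears only under an assumed two-sided alpha. A normal model with 20/30 also implies P(X>Y) = Φ((20/30)/√2) = 0.68, not the stated 0.72, but that mismatch is a separate power question and is not relied on here.

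**What to change.** In the Aim 1 analysis plan:

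1. Name GNRHa versus relugolix, by assigned arm, as the sole primary contrast for 12-month change in total plaque volume, and state its alpha and sidedness.
2. Adjust that comparison for baseline total plaque volume and ASCVD stratum.
3. Before outcome data are examined, choose either the outcome scale for a linear model or a covariate-adjusted rank-based method, and say which is primary.
4. Report comparisons with the no-ADT cohort as secondary and observational, adjusted for baseline plaque, age, statin use and ASCVD risk.

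**Cost.** Wording only for the randomised comparison: no extra men, scans or visits, since baseline plaque is measured and the stratum is needed to randomise. If both covariates prove unrelated to change, about 0.7 to 0.9 power points are lost, of which the two degrees of freedom account for only 0.05. For the no-ADT cohort, the sponsor should confirm that the ASCVD score is recorded, because those men are not randomised.

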Numerous genetic alterations have been shown to result in either enhanced or diminished ability to mount inflammatory immune responses, including genes associated with 'clonal hematopoiesis of indeterminate potential' (CHIP) such as DNMT3A, TET2, ASXL1, PPM1D, KDM6A, and BCOR⁵³⁻⁵⁵, as well as several others that alter inflammatory immune function⁵⁶⁻⁶². The impact of these immune-related genomic alterations on the development of inflammatory immunity and CV toxicity following ADT will be examined in Aim 3, testing the underlying hypothesis that **somatic mutations associated with enhanced effector responses lead to increased CV injury in men receiving GNRH agonists but not relugolix.**

5. Study Intervention/Investigational Agent

Hormone Therapy Intervention

For men who will be receiving ADT with radiation therapy, there will be a 1:1 randomization between GNRHa (i.e. leuprolide or triptorelin) versus oral relugolix. Dosing for these agents are per standard FDA-approved guidelines, and the study has no impact on dose or duration of therapy.

For men receiving GNRHa, standard FDA-approved intramuscular or subcutaneous injectable doses will apply (i.e. leuprolide 7.5 mg monthly, 22.5 mg q3month, 45 mg q6month; triptorelin 11.25 mg q3month, 22.5 mg q6month). Each patient may receive 21-30 days of oral bicalutamide 50 mg daily beginning at the time of first injection (i.e. to hinder the initial testosterone flare associated with GNRHa) at the discretion of the treating provider. Duration of therapy will depend on the risk category of prostate cancer, as detailed in section 6.

For men receiving oral relugolix, standard FDA-approved oral doses will apply (i.e. 360 mg on day 1, followed by 120 mg daily for the duration of therapy). The tablet is in doses of 120 mg, and it can be taken by mouth with or without food. If the subject misses > 7 days of medication, then a loading dose of 360 mg will be initiated followed by re-initiation of 120 mg daily thereafter. Participants will be asked to complete a drug diary and bring the diary in addition to medication for reconciliation at each follow up visit. Duration of therapy will depend on the risk category of prostate cancer, as detailed in section 6.

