Subaim 1.1. Relationship between ADT and accelerated coronary plaque development/rupture									
Subaim 1.2. How baseline cardiac imaging biomarkers correlate with ADT-associated plaque development									
Aim 2. Relationship between leuprolide versus relugolix on immune effector responses implicated in atherosclerosis									
Subaim 2.1. How pre-existing and ADT-augmented inflammatory immune responses impact CV toxicity									
Subaim 2.2. How circulating proteomic biomarkers predict for cardiac toxicity									
Aim 3. How pre-existing genomic alterations impact development of cardiac toxicity following leuprolide versus relugolix									
Subaim 3.1: Identification of how pre-existing genomic alterations impact immune responses and CV toxicity									

10. Inclusion and Exclusion Criteria

Inclusion:

- Men ≥18 years old
- Non-metastatic prostate cancer
- Non-metastatic, biochemically recurrent prostate cancer
- Plan to undergo curative-intent pelvic radiation therapy (photons or protons) with or without brachytherapy

Exclusion:

- Metastatic prostate cancer requiring >24 months of ADT
- Prior invasive cancer diagnosis
- Prior exposure to androgen deprivation therapy
- Prior exposure to chemotherapy, immunotherapy, or radiation therapy

Protocol Title: Mechanism and Predictors of Cardiotoxicity after Prostate Cancer Treatment: A Parallel Cohort and Randomized Trial Comparing Radiation Alone, Radiation plus Leuprolide, and Radiation plus Relugolix

- History of cardiac bypass surgery, percutaneous coronary intervention, or cardiac device implantation
- Renal insufficiency, contrast allergy, or arrhythmias that limits feasibility of CT acquisition

11. Vulnerable Populations

Not applicable. This study does not involve individuals who are vulnerable to coercion or undue influence, such as pregnant women, children/minors, cognitively-impaired, prisoners, etc.

12. Local Number of Participants

Our accrual goal for this protocol is 90 patients (n=30 in each arm).

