Based on current prostate cancer volume at Winship Cancer Institute, accrual is expected to be complete in 12 months. Specifically, approximately 40 new patients with localized intact or recurrent PCa eligible for XRT (with or without ADT) are seen at all Winship sites monthly. We predict an enrollment rate of 20% with a low dropout rate, given that the final blood draw and coronary CT will occur 12 months after treatment initiation, which corresponds to the time of first or second standard post-treatment follow up appointment after completion of therapy.

Clinical research coordinators will screen all prostate cancer radiation oncology providers (directed by PI [name]) for all eligible patients to enroll. Co-investigators will be responsible for consenting patients in radiation oncology clinic.

13. Recruitment Methods

Patients will be recruited from those seen at the Department of Radiation Oncology at Winship Cancer Institute (EUH, EUHM, ESJH, EPTC). A brief description of the study will be given verbally to the patients, followed by written informed consent, and any relevant supplemental material as needed. The patients will be given ample time to review the consent and a time for questions and answer will be provided.

Study Enrollment Procedures

A copy of the institution's IRB-approved informed consent document and written justification for any changes made to the informed consent for this protocol must be on file at the Online Collaborative Research Environment (OnCore, <https://oncore.emory.edu>) and available to the Emory University Office for Clinical Research) before any patients may enter. The Winship Cancer Center institution consent form must be reviewed and approved and all documents must be received (i.e., IRB approved documentation, IRB approved consent form, etc.).

Patient Registration

All patients entering this study will be registered with the Clinical Trials Office (CTO) at the Winship Cancer Institute, Atlanta, GA. The CTO is open Monday through Friday from 8am-5pm (EST). OnCore will be used to record information for all registered patients including their assigned patient ID.

Study personnel will notify Winship Central Subject Registration (WCSR) by email at [contact], once subject has been consented for a trial.

Email notification must be done within 24 hours after consent has been obtained and it will include scanned copies of:

- Signed patient consent form
- HIPAA authorization form

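### The 80% power is stated for 30 men per arm with both scans, but 30 per arm is also the enrolment target, so the figure makes no allowance for the dropout the plan expects

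*Combined protocol and SAP*

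**What the plan says.** The sample-size justification is the Power paragraph under Aim 1.1 in section 6. Its inputs are "Using a standard deviation of 30 mm³ for the change in total plaque volume" and a comparison of two arms, for which "60 participants (30 in each comparative treatment arm) with both baseline and month 12 CCTA would provide 80% power" for a difference of at least 20 mm³. The same sentence gives the effect in brackets as P(X>Y) 0.72. It states no alpha or sidedness, and the Aim 1 analysis plan names no test for the unadjusted primary comparison.

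Enrolment is given in three places, each with 30 per group: the sample-size row of section 1, the accrual forecast in section 9, and section 12, which says "Our accrual goal for this protocol is 90 patients (n=30 in each arm".

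On attrition, section 12 says "We predict an enrollment rate of 20% with a low dropout rate", with no number. Section 14 lists routes out of the study, including intercurrent illness, adverse events including death, withdrawn consent, noncompliance and loss to follow-up. It also commits the investigator to try to complete follow-up procedures after a withdrawal. The plan gives no inflation for attrition, no replacement rule and no method for a missing 12-month scan in the primary analysis.

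**The concern.** One number is doing two jobs. The power statement needs 30 men per arm with a scan at both times, and the accrual plan recruits 30 men per arm. Both hold only if every enrolled man returns for a contrast CT a year after starting cancer treatment, and the plan itself does not expect that.

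This paragraph is the only sample-size justification for the primary endpoint. The study hypothesis is that plaque progression is accelerated with GNRHa and not with relugolix, so a null comparison between the randomized arms would be informative only in proportion to the power actually achieved. Readers who take 80% at face value would over-read such a result.

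**Working it through.** **Inputs from the plan.** Difference in 12-month change: 20 mm³. SD of change: 30 mm³. Men per arm with both scans: 30. The randomized comparison is 1:1 (section 5).

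**Assumptions, because the plan is silent.** Alpha is 5%, shown one-sided and two-sided. The test is a two-sample t-test. Loss is 10% or 20%, equal in both arms, and acts only by reducing n: 30 × 0.9 = 27 and 30 × 0.8 = 24.

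**Formula.** With n men per arm, the t statistic has 2n − 2 degrees of freedom and noncentrality (20/30) × √(n/2). Power is the probability that it exceeds the critical value.

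**Reproducing the stated 80% at n = 30.** The noncentrality is 0.667 × √15 = 2.58 on 58 degrees of freedom.
- One-sided 5%: power 81.8%. A simulated Mann-Whitney test at the same effect gives 79.8%. One-sided 5% is the conventional level nearest the stated figure.
- Two-sided 5%: power 71.9% by t-test, and 69.2% by simulated Mann-Whitney. The stated figure is not reproduced.

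**Effect of losing scans (t-test).**

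| Evaluable per arm | Loss | Power, one-sided 5% | Power, two-sided 5% | Difference detectable with 80% power, two-sided 5% |
|---|---|---|---|---|
| 30 | 0% | 81.8% | 71.9% | 22.1 mm³ |
| 27 | 10% | 78.0% | 67.2% | 23.3 mm³ |
| 24 | 20% | 73.6% | 61.8% | 24.8 mm³ |

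Smaller losses at one-sided 5% give 80.6% with 29 per arm and 79.3% with 28.

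**Separating dropout from the unstated alpha.**
- One-sided, loss costs 81.8 − 78.0 = 3.8 points at 10% and 81.8 − 73.6 = 8.2 points at 20%.
- Two-sided, power is already 80 − 71.9 = 8.1 points short with no loss. At 27 per arm the total shortfall is 80 − 67.2 = 12.8 points, of which dropout adds 4.7. At 24 it is 80 − 61.8 = 18.2 points, of which dropout adds 10.1.
- The two-sided detectable difference is already 22.1 mm³ with no loss. Dropout adds 1.2 mm³ at 27 per arm and 2.7 mm³ at 24.

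**The bracketed effect.** Under normality, a difference of 20 with SD 30 gives P(X>Y) = Φ(0.667/√2) = 0.68, not 0.72. A value of 0.72 needs a standardized difference of 0.824, or 0.824 × 30 = 24.7 mm³. Noether's formula for a rank test, power = Φ(√(3N) × |P − 0.5| − 1.96) with N the total in both arms, gives the following for P = 0.72 at two-sided 5%:
- N = 60: √180 × 0.22 = 2.95, power 83.9%.
- N = 54: √162 × 0.22 = 2.80, power 80.0%.
- N = 48: √144 × 0.22 = 2.64, power 75.2%.

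**The case against.** The power sentence is conditional: it says what 30 men per arm with both scans would provide, and it does not promise that enrolling 30 delivers them. Read that way it contains no false statement, and the gap is a missing allowance, not a miscalculation. That stands.

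A reader might go further and infer that dropout shows the 80% will not be delivered under the plan's own assumptions. The documents do not support that. The only assumption is that dropout is low; 10% and 20% are not the plan's figures. At one-sided 5%, one lost scan per arm still leaves 80.6%. There are also reasons to expect good retention: the last scan is timed to a standard follow-up visit (section 12), each scan is compensated with $100 (section 17), and follow-up is to be attempted after withdrawal (section 14). None of these is an allowance, but they argue against treating 20% as the expected case.

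A reader might also infer that the 80% requires zero loss whatever alpha and test were used. That too is more than the documents show. Taking P(X>Y) 0.72 at two-sided 5%, Noether's formula keeps 80.0% at 27 per arm. The reading has its own difficulty: 0.72 does not match 20/30, it gives 83.9% instead of 80% at 30 per arm, and it falls to 75.2% at 24.

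**Conclusion.** The point holds as a missing attrition allowance. The required number of men with both scans equals the number enrolled, some loss is expected, and nothing in the plan absorbs it. As written, the 80% describes the enrolled trial only with essentially no missing 12-month scan.

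The size depends on two things the plan does not state: the dropout rate, and the alpha and test. On the t-test reading nearest the stated figure (one-sided 5%), 10% loss leaves 78.0% and 20% leaves 73.6%, so a truly low loss costs only a few points. At two-sided 5% the figures are 67.2% and 61.8%, but those should not be charged to dropout alone. The 8.1 points missing at zero loss are a separate matter: most of the gap at 27 per arm, and a little under half of it at 24.

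This should be corrected because the primary endpoint has no other sample-size justification, but it does not undermine the design.

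**What to change.** In the Power paragraph of section 6:
- Label 30 per arm as the number enrolled, and give the number expected to have both scans.
- State the expected dropout rate, alpha, sidedness and primary test. Without these, power at any evaluable number cannot be restated.
- Reconcile the 20 mm³ difference and SD of 30 mm³ with P(X>Y) 0.72, or explain the distribution under which they agree.
- Report power and the detectable difference at the expected evaluable number, for example 27 and 24 per arm, beside the zero-loss value, so that the effect of dropout can be seen apart from the choice of alpha.

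This is a change of text only. It needs no extra enrolment, scan or procedure. The cost is a power statement that will probably be less favourable than 80%.
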